6.2.3 PRODUCT STORAGE AND STABILITY

Product will be stored according to manufacturer recommendations. All unused supplement will be returned to IDS via study personnel and destroyed by IDS.

Protocol PAR-18-829

6.2.4 PREPARATION

Bottles of flavokavain AB-free kava (75 mg kavalactones/capsule) with the same lot number will be directly purchased from Thorne Research Inc. This product will be used because of its lack of flavokavains A and B (<0.2 mg/capsule) and consistent content of total kavalactones.

6.3 MEASURES TO MINIMIZE BIAS: RANDOMIZATION AND BLINDING

There is no randomization process in this study. All qualified and consented study participants will receive the same total daily dose of kava and will follow through will all follow up procedures.

6.4 STUDY INTERVENTION COMPLIANCE

Study subjects will have one day screening and one day of study intervention therefore compliance is highly achievable.

6.5 CONCOMITANT THERAPY

No concomitant medications will be allowed during this study with the exception of multi vitamins and contraception.

6.5.1 RESCUE MEDICINE

Diphenhydramine will be available for use in the case of any allergic response for subjects who have ingested the study drug.

7 STUDY INTERVENTION DISCONTINUATION AND PARTICIPANT DISCONTINUATION/WITHDRAWAL

7.1 DISCONTINUATION OF STUDY INTERVENTION

This study will be stopped prior to its completion if: (1) the intervention is associated with adverse effects that call into question the safety of the intervention; (2) difficulty in study recruitment or retention will significantly impact the ability to evaluate the study endpoints; (3) any new information becomes available during the trial that necessitates stopping the trial; or (4) other situations occur that might warrant stopping the trial. If at any time during the study the participants are found to be at excessive risk, the study will be terminated. All key research personnel have completed the required human subjects training course. Key personnel include all individuals responsible for the design and conduct of the study.

7.2 PARTICIPANT DISCONTINUATION/WITHDRAWAL FROM THE STUDY

Study subjects will be informed that they are welcome to withdrawal or discontinue the study at any time should they feel this is not their best interest, does not meet their time availability, or for any other reason they see fit. Subjects will be asked to speak with the study coordinator or the investigator to indicate their request for withdrawal and all study related activity will stop.

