1.2 SCHEMA

Week/Day (-14 to -1)

Screening

- Obtain informed consent
- Screen potential participants by inclusion and exclusion criteria
- Obtain medical history
- Height and weight
- Concomitant medication review
- Lab testing (CMP, PT/INR, Indirect bilirubin, CYP2D6)
- Urine Drug Screen
- Urine Pregnancy test (for women on child bearing potential)
- C-SSRS
- HAM-A

Visit1/Day

Baseline assessments/Study intervention

- Concomitant medication review
- Adverse event review and evaluation
- · Administer study medication
- Urine drug screen
- Urine pregnancy test (for women of child bearing potential)
- PK sampling (pre-dose, 0.5, 1, 2, 3, 4, 5, 6, 8, and 12 hours post dose)
- Lab testing (CMP)

Visit 2/Week 1

- Lab testing (CMP)
- Adverse event review and evaluation
- Concomitant medication review

Visit 3/Week 4

- Lab testing (CMP)
- Adverse event review and evaluation
- Concomitant medication review

Visit 4/Week 8

- Lab testing (CMP)
- Adverse event review and evaluation
- Concomitant medication review

Visit 5/Week 12

Final assessments

- Lab testing (CMP, PT/INR)
- Adverse event review and evaluation
- Concomitant medication review

Version 5.000

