1.3 SCHEDULE OF ACTIVITIES (SOA)

Protocol PAR-18-829

| Procedures | | Screening Day -14 to -1 | Baseline Visit 1, Day 1 | 2 | Week 4 Study Visit 3 Day 28 +/- 1 day | Week 8 Study Visit 4 Day 56 +/-1 day | Week 12/Final Visit Study Visit 5 Day 84 +/- 1 day |
|---|---|-------------------------------|-------------------------------|---|---|--|--|
| Informed consent | | X | | | | | 2 447 |
| Demographics | | Х | | | | | |
| Inclusion/exclusion review | х | Х | | | | | |
| Medical History | | Х | | | | | |
| Administer study intervention | | | Х | | | | |
| Concomitant medication review | | X | Х | | | | |
| Height and weight | | Х | | | | | |
| Vital signs | | Х | | | | | |
| CYP2D6 testing | | Х | | | | | |
| Comprehensive Metabolic Panel testing | | Х | X b | Х | X | X | X |
| PT/INR | | Х | | | | | Х |
| Urine pregnancy test ^a | | Х | Х | | | | |
| Urine drug screen | | Х | Х | | | | |
| Adverse event review and evaluation | | | Х | | | | |
| Pharmacokinetic sampling | | | Х | | | | |
| HAM-A | | Х | | | | | |
| C-SSRS | | Х | | | | | |
| Complete Case Report Forms (CRFs) | | Х | Х | X | Х | Х | X |
| a: for women of child bearing potential b: test will be performed at 12 hours post initial kava ingestion | | | | | | | |

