Management of psychiatric emergencies: We believe that the risk of psychiatric emergencies occurring during the execution of this study is low, based on the pilot data and because participants are healthy volunteers who have been pre-screened for psychiatric stability. However, should such an emergency arise (such as an acute decompensation, statement or demonstration of active suicidal ideation, violence, etc.), we have procedures in place to ensure the safety of the participant and the staff. Liver function abnormalities: We will use a kava product that has removed the potentially liver toxic elements, flavokavain A and B, and has been rigorously tested for quality. However, we will nevertheless closely monitor serum liver biochemistries (AST, ALT, ALP, bilirubin and albumin) at screening, at hour 12 post-kava ingestion, and at weeks 1, 4, 8 and 12. Although the timing of any potential liver toxicity with kava is not known, the timing of the few reported cases in the NIH liver tox database suggests that the onset of symptoms related to hepatotoxicity (including nausea, fatigue) is likely to be between 2 weeks and 12 weeks following initial ingestion. We will also encourage participants to contact the study team for any concerning symptoms that they may have for up to 6 months post-treatment to ensure that no delayed reactions, no matter how unlikely, are missed. We will carefully educate participants about symptoms to watch for throughout the study and following treatment.

Protocol PAR-18-829 11 May 2021

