4 STUDY DESIGN

4.1 OVERALL DESIGN

- To develop a pharmacokinetic model to identify the best dose and dosage regimens of flavokavain A/B free kava for its further development as a drug for the treatment of GAD
- Phase 1 Single site study
- Open-label
- An equal number of male and female subjects will be enrolled in study. All races and ethnicities will be included. A dose of supplement kava 225 mg will be administered at baseline either in a single dose or dosed at three times during the study visit. Study group-Pharmacokinetics is a single day intervention with 12 week follow up post study drug ingestion. Ten subjects will be recruited and enrolled into the pilot pharmacokinetic study. Each subject will stay in the out-patient Clinical Research Center (CRC) at the CTSI during the 12 hour study period. Participants will be asked to refrain from food, liquids other than water, and medications for 12 hours prior to entering the Clinical Research Center of the UF CTSI. They will have an indwelling venous catheter placed in the lower arm to facilitate the multiple blood collections during the study. Each subject will take three 75 mg kava capsules and ten blood draws (2 mL EDTA vacutainer) will be collected corresponding to the absorption, distribution, metabolism and excretion phase of the pharmacokinetic curve. Specifically, blood will be withdrawn at baseline and 0.5, 1, 2, 3, 4, 5, 6, 8 and 12 hours after kava ingestion. The blood samples will be processed and then stored at -80°C till analysis. The period of follow up for any delayed adverse effects (e.g., monitoring of liver function) will be extended such that all participants will be followed for a full 12 weeks after their last kava ingestion. CYP2D6 testing will be conducted to determine if the genotype affects the pharmacokinetics of kava.

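### Section 7.2 does not separate stopping kava and PK sampling from stopping safety follow-up, so a dosed participant who withdraws is not offered the remaining liver tests (minor)

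*Combined protocol and SAP*

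**What the plan says.** Section 7.2 lets a participant leave at any time and for any reason. The participant speaks with the coordinator or the investigator "to indicate their request for withdrawal and all study related activity will stop". No early-termination visit or remaining safety test is offered there, and none is offered to withdrawn participants elsewhere in the protocol.

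Other sections set out follow-up without saying what happens after withdrawal:

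- Section 4.1 states that "all participants will be followed for a full 12 weeks after their last kava ingestion". The synopsis and 6.1.1 repeat this.
- Section 2.3.3 schedules liver biochemistries "at screening, at hour 12 post-kava ingestion, and at weeks 1, 4, 8 and 12". The footnote to the schedule of activities (1.3) fixes the Day 1 panel: "test will be performed at 12 hours post initial kava ingestion".
- Section 2.3.3 also says that the onset of hepatotoxicity symptoms "is likely to be between 2 weeks and 12 weeks following initial ingestion", and it encourages participants to contact the team "for any concerning symptoms that they may have for up to 6 months post-treatment".
- The schema (1.2) shows Visits 2 to 5 as a metabolic panel (CMP), adverse-event review and medication review, with PT/INR added at Week 12. Section 8.2 gives safety monitoring as the purpose of the laboratory tests.
- Section 7.1, despite its title, covers stopping the whole study, not stopping the intervention in one person.

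**The concern.** Kava is given on one day only (4.1, 6.4). Once the last capsule is taken, ending all activity spares no exposure. After Day 1 it removes only safety checks, which sits badly with the 12-week commitment in 4.1. The protocol has no route by which a person can stop dosing and PK sampling but stay in safety follow-up.

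This matters most on Day 1. Section 4.1 says "Each subject will stay in the out-patient Clinical Research Center (CRC) at the CTSI during the 12 hour study period", with an indwelling catheter and ten blood draws. Someone who cannot tolerate that day, or runs out of time, might still accept single-draw visits later. As written, 7.2 does not ask. What would be missed is a symptom-free rise in liver enzymes: the action rule in 9.4.4 (above 3 times the upper limit on two measures, or above 5 times once) cannot be triggered in someone who is no longer tested.

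**Working it through.** **Inputs.** Enrolment is 10 (4.1). Post-dose liver tests are at hour 12 and Weeks 1, 4, 8 and 12 (2.3.3). Anticipated loss to follow-up is 20% (7.3). The daily dose is three 75 mg capsules, taken at once or at three times (4.1, 6.2.1).

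**The plan's own figure.** 0.20 × 10 = 2, which agrees with the N=2 in 7.3. That figure pools unresponsive people with people who have stopped taking part, so it is not a count of withdrawals.

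**Tests planned.** Each participant has 5 post-dose tests, so 10 × 5 = 50 in all. Three of the five (Weeks 4, 8 and 12, or Days 28, 56 and 84) fall between 2 and 12 weeks, so 10 × 3 = 30.

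**Tests lost per person, by time of request:**

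| Request made | Lost, of 5 post-dose | Lost, of Weeks 4, 8, 12 |
|---|---|---|
| During Day 1 stay, before the hour-12 panel | 5 | 3 |
| After hour 12, before Week 1 | 4 | 3 |
| Between Weeks 1 and 4 | 3 | 3 |
| Between Weeks 4 and 8 | 2 | 2 |
| Between Weeks 8 and 12 | 1 | 1 |

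**Range over the study.** The number of withdrawals, k, is not in the documents. Taking k = 0, 1 or 2 as an assumption:

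- Week 4 to 12 tests lost: 0, 1 to 3, or 2 to 6 of 30. The maximum is 2 × 3 = 6, and 6/30 = 20%. If both people leave just after Week 4 it is 2 × 2 = 4 (13%); just after Week 8, 2 × 1 = 2 (7%).
- All post-dose tests lost: 0, 1 to 5, or 2 to 10 of 50. The maximum, 2 × 5 = 10 (20%), needs both people to leave before hour 12.

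**What an offer could recover.** Recovered = uptake × lost. For the worst case of 6, uptake of 0%, 50% or 100% gives 0, 3 or 6 tests. The uptake values are assumptions with no source in the documents.

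**Exposure spared by stopping.** After the last capsule: 0 mg. After the first of three divided doses: 225 − 75 = 150 mg. The fix must keep that second benefit.

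**Absolute risk.** Section 2.3.1 gives less than 1 liver injury per 1,000,000 daily doses, based on reported cases. For ten people dosed on one day: 10 × 1/1,000,000 = below 0.001% for the whole study. For two withdrawals: below 0.0002%. The same section says the true frequency is not known, and the rate concerns reported injury, not silent enzyme rises. The figure of below 0.03% in 2.2 is for the whole R61 phase, which also includes the biomarker work (10.1.11), so it is not the figure for this one-day study.

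**The case against.** The strongest objection is that, after Day 1, the study consists only of the visits the fix would offer again. A person who withdraws at Week 2 or Week 6 is declining exactly those draws. This stands. Four of the five rows in the table describe such people, and most of the possible gain lies in the Day 1 row.

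It can also be said that nothing in 7.2 forbids staff from offering a safety test during the withdrawal conversation, that known events are followed to resolution or stabilization (8.3.4), and that participants can report symptoms for 6 months (2.3.3). These provisions soften the gap for symptomatic cases. They do not find a silent enzyme rise: the contact depends on the participant noticing something, and event follow-up needs an event already identified. The consent form is not in the copy reviewed, so what participants are told about tests after withdrawal is unknown.

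The 12-week sentence in 4.1 might be read as overriding 7.2. It is a general statement of intent, whereas 7.2 is the specific withdrawal rule. At best the two conflict and staff must choose.

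Two stronger readings are tempting. A reader might infer from 7.3 that 20% of the liver tests will be lost through this rule. The documents do not support that: 7.3 includes unresponsive people, whom no rewording of 7.2 would reach, and zero withdrawals fits the text equally well. A reader might also infer that the three later tests cover the likely window for silent enzyme rises. Section 2.3.3 gives its window for the onset of symptoms; the documents give no timing or rate for symptom-free rises.

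**Conclusion.** The point holds as a minor one. Followed as written, 7.2 ends safety-only monitoring after a one-day exposure, and this is at odds with the stated 12-week follow-up of all participants. The clear case is withdrawal during the Day 1 stay, which leaves 0 of 5 post-dose liver tests. For later withdrawals the practical gain is small.

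The ceiling is 6 of 30 Week 4 to 12 tests. It rests on the assumption that both anticipated losses are active withdrawals by dosed participants before Week 4. The protocol's own rates make it very unlikely that a lost test hides an injury.

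A reader might infer harm to the primary endpoint. Withdrawal after Day 1 leaves the half-life data untouched, because PK sampling is finished by then. Withdrawal during the stay would cost PK samples, but the proposed wording does not change that.

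**What to change.** In 7.2, replace the clause that stops all activity with wording such as: *no further kava is given and no further PK samples are drawn; any participant who has taken kava is offered the remaining scheduled CMP and AE checks through Week 12 (PT/INR at Week 12), and whatever the participant declines stops.* Make the same offer to participants withdrawn by the study team, for whom 2.3.3 provides treatment or referral but does not mention the scheduled liver tests.

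This keeps the right to stop everything, and still spares the remaining capsules when someone in the divided-dose group leaves between doses. The cost is one or two sentences, a short IRB-approved amendment and matching consent wording. The draws are optional and already planned: at most 4 per person who withdraws after Day 1, or 5 if the request comes during the stay and the hour-12 panel is accepted.

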7.3 LOST TO FOLLOW-UP

NCCIH considers lost to follow-up as a research subject who was participating in the study at a certain point in time and subsequently missed two consecutive study visits and is unresponsive to study contact, or is no longer participating in study activities. The anticipated lost to follow-up rate for this study will be 20% of total enrolment (e.g., N=2).

8 STUDY ASSESSMENTS AND PROCEDURES

8.1 EFFICACY ASSESSMENTS

There is no intention of determining efficacy during this phase of the study.

8.2 SAFETY AND OTHER ASSESSMENTS

All subjects will undergo lab testing at various time points. Before ingestion of kava and at weeks 1, 4, 8, and 12 to monitor for safety.

8.3 ADVERSE EVENTS AND SERIOUS ADVERSE EVENTS

8.3.1 DEFINITION OF ADVERSE EVENTS (AE)

An adverse event (AE) is any untoward medical occurrence in a subject during participation in the clinical study or with use of the experimental agent being studied. An adverse finding can include a sign, symptom, abnormal assessment (laboratory test value), or any combination of these regardless of relationship to participation in the study.

8.3.2 DEFINITION OF SERIOUS ADVERSE EVENTS (SAE)

A serious adverse event (SAE) is one that meets one or more of the following criteria:

- Results in death
- Is life-threatening (places the subject at immediate risk of death from the event as it occurred)
- Results in inpatient hospitalization or prolongation of existing hospitalization
- Results in a persistent or significant disability or incapacity
- Results in a congenital anomaly or birth defect
- An important medical event that may not result in death, be life threatening, or require hospitalization
 may be considered an SAE when, based upon appropriate medical judgment, the event may jeopardize
 the subject and may require medical or surgical intervention to prevent one of the outcomes listed in this
 definition.

8.3.3 CLASSIFICATION OF AN ADVERSE EVENT

Any undesirable and unintended (although not necessarily unexpected) effect occurring as a result of interventions, interactions, or collection of identifiable private information in research. In medical research, any untoward physical or psychological occurrence in research, including abnormal laboratory finding, symptom, or disease temporally associated with the use of (although not necessarily related to) a medical treatment or procedure. Adverse events involving drugs are also referred to as adverse drug experiences. The PI will review and access for any adverse event classification in this study.

8.3.3.1 SEVERITY OF EVENT

Protocol PAR-18-829

The following scale will be used to grade adverse events:

- 1. Mild: no intervention required; no impact on activities of daily living (ADL)
- 2. Moderate: minimal, local, or non-invasive intervention indicated; moderate impact on ADL
- 3. Severe: significant symptoms requiring invasive intervention; subject seeks medical attention, needs major assistance with ADL

8.3.3.2 RELATIONSHIP TO STUDY INTERVENTION

To assess relationship of an event to study intervention, the following guidelines are used:

- 1. Related (Possible, Probable, Definite)
 - 1. The event is known to occur with the study intervention.
 - 2. There is a temporal relationship between the intervention and event onset.
 - 3. The event abates when the intervention is discontinued.
 - 4. The event reappears upon a re-challenge with the intervention.
- Not Related (Unlikely, Not Related)
 - 1. There is no temporal relationship between the intervention and event onset.
 - 2. An alternate etiology has been established.

8.3.3.3 EXPECTEDNESS

The Study PI and Independent Monitoring Committee will be responsible for determining whether an SAE is expected or unexpected. An adverse event will be considered unexpected if the nature, severity, or frequency of the event is not consistent with the risk information previously described for the intervention.

8.3.4 TIME PERIOD AND FREQUENCY FOR EVENT ASSESSMENT AND FOLLOW-UP

Unanticipated problems will be recorded in the data collection system throughout the study. The PI will record all reportable events with start dates occurring any time after informed consent is obtained until 7 (for non-serious AEs) or 30 days (for SAEs) after the last day of study participation. At each study visit, the investigator will inquire about the occurrence of AE/SAEs since the last visit. Events will be followed for outcome information until resolution or stabilization.

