1 PROTOCOL SUMMARY

1.1 SYNOPSIS

A Phased Clinical Trial of a Dietary Supplement Kava: Biomarker Title:

Changes and Anxiolytic Effects

Study Description:

Objectives: Primary Objective: To characterize pharmacokinetics of

flavokavain A/B free kava.

Secondary None

Objectives:

Endpoints: Primary Endpoint: Examining the half life of each of the six major

kavalactones.

Secondary None

Endpoints:

Study Population: We will recruit 10 healthy participants. There are no restrictions on

> ethnicity, social background, or gender. All subjects must meet the following criteria at baseline to be eligible for participation in the pharmacokinetic study (a) be between the ages of 18 and 50 years (b)

The University of Florida Clinical Research Center will be used to

enroll participants and conduct research procedures. This facility is

Females of potential childbearing status must use adequate

contraceptive precautions.

Phase:

Description of Sites/Facilities

Enrolling Participants: designed for clinical research.

Description of Study Intervention:

Ten subjects will be recruited and enrolled into the pilot pharmacokinetic study. Each subject will stay in the out-patient Clinical Research Center (CRC) at the CTSI during the 8-h study period. Participants will be asked to refrain from food, liquids other than water, and medications for 12 hours prior to entering the Clinical Research Center of the UF CTSI. They will have an indwelling venous catheter placed in the lower arm to facilitate the multiple blood collections during the study. Each subject will take three 75 mg kava capsules and ten blood draws (2 mL EDTA vacutainer) will be collected corresponding to the absorption, distribution, metabolism and excretion phase of the pharmacokinetic curve. Specifically, blood will be withdrawn at baseline and 0.5, 1, 2, 3, 4, 5, 6, 8, and 12 hours after kava ingestion. The blood samples will be processed and then stored at -80°C till analysis. The period of follow up for any delayed adverse effects (e.g., monitoring of liver function) will be extended such that all participants will be followed for a full 12 weeks after their last kava ingestion.

A Phased Clinical Trial of a Dietary Supplement Kava: Biomarker Changes and Anxiolytic Effects Phase

1: Kava Pharmacokinetics

Protocol PAR-18-829 11 May 2021

Study Duration: 24 weeks **Participant Duration:** 12 weeks

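### The adverse event recording window in 8.3.4 closes about 13 weeks (non-serious) or 16 weeks (serious) after dosing, short of the 6-month reporting invitation in 2.3.3

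*Combined protocol and SAP*

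**What the plan says.** Section 2.3.3, under liver function abnormalities, encourages participants to "contact the study team for any concerning symptoms that they may have for up to 6 months post-treatment", and gives the reason: "to ensure that no delayed reactions, no matter how unlikely, are missed". The same paragraph puts the onset of hepatotoxicity symptoms, with nausea and fatigue as examples, as "likely to be between 2 weeks and 12 weeks following initial ingestion".

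Section 8.3.4 sets the period for recording. The investigator records reportable events that start after consent and "until 7 (for non-serious AEs) or 30 days (for SAEs) after the last day of study participation". Events already captured are followed until they resolve or stabilise. The section opens by saying that unanticipated problems are recorded for as long as the study runs.

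Participation lasts 12 weeks. The synopsis (1.1) says that "all participants will be followed for a full 12 weeks after their last kava ingestion", section 4.1 describes a "single day intervention with 12 week follow up post study drug ingestion", and the last column of the schedule of activities (1.3) is "Study Visit 5 Day 84 +/- 1 day".

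No section says how an ordinary adverse event that starts after the 8.3.4 window, but within the 6 months of 2.3.3, is to be recorded, graded or reported.

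**The concern.** The two sections serve the same aim but end at different times. The 6-month invitation exists to catch reactions later than expected; the recording rule ends well before it. A participant who telephones in month 5 with new fatigue or nausea has done what the protocol asked, yet nothing in 8.3.4 requires the event to be entered. Such symptoms are non-serious unless they meet a criterion in 8.3.2, so the shorter 7-day limit applies to the very symptoms given as examples.

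Later steps depend on that entry. The annual summaries in 8.3.5 and 8.3.6 cover events that the trial has documented, and the tables for the monitors are built from the study's safety data. If a late event is left out, the safety summary is incomplete on the one organ system for which the protocol extended follow-up.

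A second difficulty is the anchor. The window runs from the last day of participation, not from ingestion, so it shortens for anyone who leaves early. Section 7.3 anticipates losing 2 of 10.

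**Working it through.** The protocol gives no figure for this gap, so there is nothing to reproduce; the check is a day count.

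**Inputs**
- Dosing on Day 1 (1.3; single day, 4.1).
- Final visit on Day 84, plus or minus 1 day (1.3), that is 83 days after dosing (range 82 to 84).
- Recording ends 7 days (non-serious) or 30 days (serious) after the last day of participation (8.3.4).
- Contact period of 6 months post-treatment (2.3.3). The length in days is my assumption: 182 days (26 weeks), with 183 days and 168 days (24 weeks) as alternatives.

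**Formulae**
- End of recording (days after dosing) = final visit (days after dosing) + 7 or + 30.
- Gap = 6 months in days − end of recording.

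**Completer seen on Day 84**
- Non-serious: 83 + 7 = 90 days after dosing (Day 91). Gap = 182 − 90 = 92 days; 92/182 = 51%.
- Serious: 83 + 30 = 113 days after dosing (Day 114). Gap = 182 − 113 = 69 days; 69/182 = 38%.

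**Sensitivity over the visit window**

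| 6 months read as | Gap, non-serious (days) | Gap, serious (days) |
|---|---|---|
| 168 days | 77 to 79 | 54 to 56 |
| 182 days | 91 to 93 | 68 to 70 |
| 183 days | 92 to 94 | 69 to 71 |

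The gap remains on every reading.

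**Against the expected onset range.** Two to 12 weeks is 14 to 84 days after ingestion. For completers, even the earliest end of recording (82 + 7 = 89 days) is later than 84 days, so the whole range is covered. Serious-event recording runs 113 − 84 = 29 days beyond it.

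**Early leaver.** Take a participant whose last day of participation is the dosing visit, and assume that 8.3.4 counts from that day (the section does not say). Non-serious recording ends at 0 + 7 = 7 days, before the range opens at 14. Serious recording ends at 0 + 30 = 30 days, which covers 30 − 14 = 16 of the 84 − 14 = 70 days in the range. This is the extreme case; later departures cover more.

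**The case against.** The strongest reply is that a reader might infer that late events will go unrecorded and never reach the monitors, and the documents do not say that. Section 8.3.4 sets when recording is required; it does not forbid later entries. Several provisions carry no 7- or 30-day limit:
- Section 8.3.6 sends serious, unanticipated, possibly related events to the monitors, the IRB, the FDA and NCCIH.
- Section 8.4.2 does the same for unanticipated problems (without the FDA), within 7 or 14 days of awareness.
- Section 2.3.3 makes the medical monitor responsible for passing every adverse event to the data safety monitoring board.
- Section 10.1.6 has that board review reported serious events.

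Liver injury is a listed risk (2.3.1), so expectedness could be argued. But 8.3.3.3 also counts an event as unexpected when its severity or frequency does not fit the described risk. One case among 10 single-day recipients would plausibly qualify against a rate below 1 per million daily doses.

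This stands for serious, unexpected, possibly related events. It does not cover the rest. Late non-serious events, and serious ones judged expected or unrelated, do not meet the conditions of 8.3.6 or 8.4.1. The medical monitor's general duty does not say that such events enter the database or the summaries.

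A second reply is that a participant who calls late still reaches clinicians, so the invitation keeps its protective value. That also stands; what is lost is assured capture in the data.

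A third is that the expected onset lies inside the window, only 10 people are dosed, and 2.2 puts the hepatotoxicity risk below 0.03% in this phase. For completers this is right, and it keeps the point small.

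Finally, the last day of participation might be read to include the 6 months. The 12-week participant duration in 1.1 and the final visit at Week 12 in 1.3 speak against that.

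**Conclusion.** The inconsistency between 2.3.3 and 8.3.4 is real, and its effect is minor. For completers, late non-serious events and late serious events judged expected or unrelated fall outside the routine recording rule for about 92 and 69 days of the 6-month contact period.

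Those spans, 51% and 38% of 182 days, measure calendar time. A reader might take them as the share of liver risk left uncovered; the protocol's own 2 to 12 week onset range does not support that, because completers are covered throughout it. The gap matters more for a participant who leaves early, whose window may close before or early in that range.

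The conclusion assumes that participation ends at the Week 12 visit or at withdrawal, that 6 months is about 182 days, and that staff follow 8.3.4 as written without adding events at their discretion. The primary pharmacokinetic results are unaffected.

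**What to change.** Reconcile 8.3.4 with 2.3.3. State in 8.3.4 that events reported through the 6-month contact route, at least those possibly related to kava, are recorded in the adverse event database and included in the monitors' reports up to 6 months after the last kava ingestion, whatever the participant's last day of participation. Anchoring to ingestion brings in voluntary reports from people who left early. Limiting the addition to possibly related events would be enough to match the purpose in 2.3.3; extending it to all spontaneous reports is optional.

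On the reckoning above, recording would run about 92 days longer for non-serious events and 69 days longer for serious ones in completers. The cost is a sentence or two in 8.3.4 and an adverse event form that stays open longer. No visits, laboratory tests or active questioning are added.
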